D.3. Setting: Einstein and Montefiore Division of Substance Abuse (DoSA). DoSA is a clinical, research, and teaching division of Einstein's Department of Psychiatry and Behavioral Sciences. DoSA operates a comprehensive substance abuse treatment program providing pharmacotherapy and related services to about 4200 adults (≥ 18 years) with current narcotic addiction (typically heroin). The primary focus is treatment of opiate dependence with methadone, and the average methadone pick-up schedule is 5 times per week. At present, DoSA operates 12 clinics in 5 Bronx communities. The treatment paradigm relies on integrating general and HCV- and HIV-related medical, substance abuse, and mental health services under one roof. Multiple RCTs have been conducted in DoSA. Both recruitment and research visits will occur at DoSA. With [name] (HCV Medical Director), [name] (DoSA Research Director), and [name] (DoSA Medical Director), participant recruitment and private office space for research visits will be ensured.

D.4. Participants. Most DoSA patients are Hispanic (59%) or black (24%), male (62%), and live under the federal poverty line (81%). Mean age is 47 years. Approximately 65% (n=2730) are HCV-infected, and 75% of those have chronic HCV (n=2048); 70% have genotype-1 (n=1434), and 80% of those are HIV-negative (n=1147). We anticipate 800 new admissions over the 3-year recruitment period, representing another 216 HCV-monoinfected genotype-1 patients.

Table 1. Inclusion and Exclusion Criteria (also see Human Subjects)

Inclusion Criteria	Exclusion Criteria

 HIV-negative Willing to receive HCV treatment on-site Initiating treatment with fixed dose (sofosbuvir and ledipasvir) Receiving methadone in clinic at least once per week Age 18 or older Able to provide informed consent English or Spanish speaking 	
 Pregnant or breast-feeding

D.5. Recruitment. Recruitment (as with other successful studies conducted in this setting)^{129,132,142} will be both active and passive; for active recruitment DoSA medical providers will inform genotype-1 HCV-infected subjects about the study and assist with referral, and for passive recruitment subjects will self-refer. Self-referred subjects will meet with their provider to determine whether starting HCV treatment is appropriate.

Determination of eligibility.

Initial screening visit and informed consent:

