groups of approximately equal size. Because of the historical importance of IL28B genotype and stage of liver disease (cirrhosis v. no cirrhosis) in determining virologic outcomes,⁴⁶ we will stratify by these 2 factors. All subjects will have the IL28B genetic test performed as per our standard clinical algorithm. To determine presence of cirrhosis, all subjects will have 2 biomarker tests (APRI and Fibrosure) performed at baseline,¹⁴³⁻¹⁴⁴ per our standard clinical algorithm (Appendices A and D). Liver biopsy / Fibroscan is not required but will be performed if 1) biomarker tests are inconclusive for determination of cirrhosis as per the SAFE algorithm (<20%),¹⁴⁵ 2) to rule out co-occurring liver disease, or 3) if the result will influence the decision to initiate treatment. Results of liver biopsy / Fibroscan (if done) will be used for stratification instead of biomarker tests. Since IL28B explains much of the variability in response between African Americans and non-African Americans,^{96,146} and rates of SVR with DAAs may be equivalent in Latinos and non-Latino Whites,⁴⁶ we will not stratify by race or ethnicity, but will adjust in the analyses if necessary.

D.8. Treatment arms: TAU, mDOT, and CGT. All 3 models of care include co-located on-site care including HCV care, primary care, and substance abuse treatment. Table 2 summarizes similarities and differences between the 3 models. Subjects randomized to TAU will receive all medications monthly at the clinic from the clinic nurse, packaged in 7-day blister packs (oral medications)

Table 2: Element	IMB Model	TAU	mDOT	CGT
Co-located care	Information Motivation	X	X	X
Enhanced social support by providers	Motivation		Nurse – individual	Medical provider - group
DOT Interferon	Behavioral Skills		Nurse - individual	Medical provider - group
DOT telaprevir and ribavirin	Behavioral Skills		DAA 1-6 doses/week	
DOT snack (if telaprevir or RBV only)	Behavioral Skills		Nurse - individual	
Enhanced social support by patients	Motivation			Peers – group
Enhanced education	Information			Weekly educational sessions
Enhanced side effect management	Information Motivation		Nurse - individual	Weekly group treatment

D.8.1. Intensive treatment intervention arms (mDOT and CGT)

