D.12.6. Cost and Cost-effectiveness Analyses. To project future HCV costs and life expectancy, we will adapt to the study population a computer simulation model of HCV disease progression that has been developed by [name] based on published data using empiric calibration methods.¹⁷¹⁻¹⁷² The model is currently being updated with data on disease progression and resource utilization from a racially diverse cohort of over 600 HCV-infected individuals cared for at Boston Medical Center, an urban public hospital system, including IDUs in methadone treatment and active IDUs.¹⁷³ The model simulates chronic HCV with fibrosis progression through 3 stages of liver fibrosis including: mild to moderate fibrosis, cirrhosis, and decompensated cirrhosis. At all stages, HCV infection is associated with increased resource utilization and decreased quality of life (QOL).^{136,186-187} When HCV infection reaches the stage of cirrhosis, individuals begin to experience increased mortality attributable to liver disease.¹⁸⁸ With successful HCV therapy, disease progression halts, and mortality, resource utilization, and quality of life returns to that of HCV un-infected individuals.¹⁸⁹ HCV-related QOL is stratified by fibrosis stage, and costs of chronic HCV care (such as hospitalizations, ED visits, and clinic visits) are identified separately for patients with and without cirrhosis and stratified by age and sex.

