We will use the model to assess the cost-effectiveness of the 3 interventions: TAU, mDOT, and CGT. Primary outcomes will be projected life-expectancy, quality-adjusted life-expectancy (QALYs), lifetime costs, and incremental cost-effectiveness ratios measured in \$/QALY. We will forecast health and cost outcomes of each intervention for a hypothetical cohort of HCV patients using baseline study data on fibrosis, age, sex, and alcohol use, and study outcome data for each intervention including SVR, resistance, and retention in care. We will explore the potential impact of resistance mutations by varying the efficacy of subsequent HCV retreatment for patients with resistance who choose to be retreated. Lifetime costs will include the costs of the intervention received as well as projected future costs of HCV care depending on treatment effectiveness. Incremental cost effectiveness ratios will be calculated for TAU compared to no treatment and for mDOT and CGI compared to the next most expensive intervention, with costs and QALYs discounted at 3% annually according to standard practice.¹⁷³ The resulting ratios will be compared to a threshold of \$100,000 per QALY.¹⁷⁴⁻¹⁷⁵ To explore uncertainties in our results, we will perform one and 2-way sensitivity analyses on key input variables (e.g. probability of SVR and intervention cost) and probabilistic sensitivity analyses (PSAs) using second order Monte Carlo simulation on multiple variables.¹⁷⁶ For PSAs we will perform 1,000 simulations of a cohort of 100,000 individuals. The result will be a distribution of 1,000 model-based outcomes with a median and interquartile range that reflects underlying uncertainty in critical model parameters.

D.13 Power considerations Assuming a conservative attrition rate of 20%, 50 subjects per arm will begin the study, but 40 subjects per arm will complete it. For power calculations for repeatedly measured continuous or binary adherence outcomes, we will use the expected number of observations per subject. The power analysis is conducted based on the omnibus testing of equality across the three groups. It follows that at least one of the post-hoc pair-wise tests is powered to be rejected by this study design.

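### The cost-effectiveness model gives every cured patient never-infected mortality, cost and quality of life whatever the fibrosis stage, so cures in cirrhosis may be over-credited

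*Combined protocol and SAP*

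**What the plan says.** D.12.6 describes a simulation model with "3 stages of liver fibrosis including: mild to moderate fibrosis, cirrhosis, and decompensated cirrhosis". Liver mortality enters at the second of these: "When HCV infection reaches the stage of cirrhosis, individuals begin to experience increased mortality attributable to liver disease". The rule after cure is "With successful HCV therapy, disease progression halts, and mortality, resource utilization, and quality of life returns to that of HCV un-infected individuals", with no exception by stage. The next sentence does vary by stage, but it is worded for ongoing infection: "HCV-related QOL is stratified by fibrosis stage, and costs of chronic HCV care".

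Patients with cirrhosis are in scope. D.7 stratifies randomization by cirrhosis, the only exclusion listed in Table 1 (D.4) is "Pregnant or breast-feeding", and D.12.6 builds the simulated cohort "using baseline study data on fibrosis, age, sex, and alcohol use".

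QALYs, lifetime costs and incremental ratios are the primary outcomes of this analysis. They are discounted at 3% a year, and the ratios are judged against $100,000/QALY. TAU is compared with no treatment, and mDOT and CGT with the next most expensive option. One-way, two-way and probabilistic sensitivity analyses are planned, with SVR probability and intervention cost as examples. The efficacy of retreatment after resistance will also be varied. Risk remaining after SVR is not named.

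**The concern.** If progression halts, a patient cured at cirrhosis remains at cirrhosis. Giving that patient the mortality, cost and quality of life of someone never infected assumes that the whole excess carried by the stage disappears with the virus. The protocol's opening section claims less, namely slower liver disease and longer survival after SVR.

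Because liver mortality in this model begins at cirrhosis, a cure at that stage can be expected to earn a large share of the QALY gain. Any residual excess left out is concentrated there. As described, the rule is also structural: there is no stage-specific post-SVR value for a sensitivity analysis to vary. The point does not depend on reinfection. At stake are the Aim 3 ratios; the Aim 1 comparisons are untouched.

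**Working it through.** **The plan's own figures.** The documents give no projected QALY gain, cost result or ratio for Aim 3, so none can be reproduced. The nearest planning figure is the SVR difference in D.13: 70% in each intensive arm against at most 40% in TAU, with power above 80%. For a three-group chi-square test with 40 per arm and alpha 0.05 (assumed), the mean rate is 0.60 and the noncentrality is 40 × (0.01 + 0.01 + 0.04)/(0.60 × 0.40) = 10.0. With 2 degrees of freedom, power is 81.5%, which agrees. The planned difference of 0.30 is used below.

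**Check 1: life-years per cure at cirrhosis, closed form.** Let a be background mortality plus the 3% discount rate, e the liver excess and r the share of e that persists after SVR. Discounted life-years are 1/(a + e) without cure, 1/a under the plan's rule and 1/(a + r·e) with a residual. The gain under the plan's rule divided by the gain with a residual is (a + r·e)/(a(1 − r)).

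Example with background 0.02 and e = 0.04, so a = 0.05:
- No cure: 1/0.09 = 11.1.
- Full return: 1/0.05 = 20.0, a gain of 8.9.
- r = 0.25: 1/0.06 = 16.7, a gain of 5.6.
- Ratio: 0.06/(0.05 × 0.75) = 1.60, an overstatement of 60%.

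Over background mortality of 1-3% and liver excess of 2-4% (both assumed), the overstatement is 15-22% at r = 0.10, 44-67% at r = 0.25 and 133-200% at r = 0.50. These figures apply to patients with cirrhosis only, not to the cohort.

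**Check 2: cohort QALYs per cure.** This is an annual-cycle model with the plan's three stages, starting age 47 (the clinic mean in D.4) and 3% discounting. All other inputs are assumed:
- Background mortality 1% at age 47, rising exponentially at 0.085 per year of age.
- Excess mortality 3% in cirrhosis and 18% when decompensated.
- Progression 3% a year to cirrhosis and 5% a year to decompensation.
- Uninfected utility 0.80, with losses of 0.05, 0.12 and 0.25 by stage.
- Uninfected annual cost $6,000, plus $1,500, $4,000 and $20,000 by stage.

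Patients start with mild to moderate fibrosis or with cirrhosis. For those cured at cirrhosis, r scales excess mortality, decompensation, utility loss and cost; r = 0 is the plan's rule. A cure before cirrhosis is worth 2.04 QALYs. A cure at cirrhosis is worth 6.36, 4.56 or 2.77 at r = 0, 0.25 or 0.50.

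| Cirrhosis share | r = 0 | r = 0.25 | r = 0.50 |
|---|---|---|---|
| 10% | 2.48 | 2.30 (−7%) | 2.12 (−15%) |
| 20% | 2.91 | 2.55 (−12%) | 2.19 (−25%) |
| 40% | 3.77 | 3.05 (−19%) | 2.33 (−38%) |

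**Check 3: ratios.** Ratio = (added cost − d × saving per cure)/(d × QALYs per cure), where d is the SVR difference. At 20% cirrhosis the saving per cure is $26,674 at r = 0 and $23,253 at r = 0.50. Results use unrounded QALYs.

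- d = 0.30, added cost $5,000: cost-saving under both rules. At $10,000: about $2,300 v. $4,600/QALY.
- d = 0.05, added cost $5,000: $25,200 v. $35,100/QALY.
- d = 0.02, added cost $5,000: (5,000 − 533)/(0.02 × 2.91) gives $76,800; (5,000 − 465)/(0.02 × 2.19) gives $103,600/QALY.

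The last pair crosses the threshold. At 10% cirrhosis the same case also crosses ($90,200 v. $106,200). At 40% it does not ($59,300 v. $98,700), and at r = 0.25 it does not for any of the three shares.

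At 20% cirrhosis, the added cost per patient at which the ratio reaches $100,000, r = 0 v. r = 0.50, is $95,200 v. $72,700 at d = 0.30, $15,900 v. $12,100 at d = 0.05, and $6,300 v. $4,800 at d = 0.02. Only an added cost between the two values in a pair changes the verdict.

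**TAU against no treatment.** Take $90,000 for the drug course (B.8 says it may be higher), 95% SVR (D.9.6 says above 95%), no other treatment costs, and the per-cure values at 20% cirrhosis. The ratio is (90,000 − 0.95 × 26,674)/(0.95 × 2.91), about $23,400, under the plan's rule and about $32,700 at r = 0.50. That is roughly 40% higher but well under the threshold.

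**The case against.** The model can be read as coherent. D.12.6 attaches excess mortality to infection that has reached cirrhosis, so removing the excess when infection clears is an optimistic simplification, not necessarily a contradiction. The rule carries a citation that cannot be checked here, and the section is a short summary of a published model still being updated. No passage says how much liver risk remains after SVR. This stands: the documents support saying that cures in cirrhosis may be over-credited, not that they are.

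A reader might also infer that the $100,000/QALY verdict is biased toward mDOT and CGT. The documents do not support that. The rule applies to cures in every arm. With equal SVR it adds nothing to the increment, and with fewer cures in an intensive arm it works against that arm. If TAU failures are later retreated and cured, they receive the same credit. The plan does expect more cures in the intensive arms, but D.13 says the effect with the current regimen is likely to be smaller, and D.9.6 puts SVR with it above 95%.

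Finally, the sensitivity analyses are open-ended and could include residual risk. That stands only in part: nothing commits the plan to it, and the rule as written provides no parameter to vary.

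**Conclusion.** The point holds as a modelling-specification weakness. A rule with no stage condition is applied to a cohort that includes cirrhosis, and no planned analysis is named that would test it. If some excess persists, the ratio is too favourable to the strategy with more cures. TAU against no treatment is exposed whatever the difference between arms; mDOT or CGT against TAU is exposed only if they achieve more SVR.

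The size rests almost wholly on assumptions, since only the stages, the starting age, the discount rate, the threshold and the planned SVR difference come from the documents. A reduction in QALYs per cure of about 7-38% is an illustration, not an estimate. A shifted ratio is also not a changed conclusion: in the cases run, the verdict was stable at the planned difference of 0.30 and crossed $100,000 only at a difference of 0.02 with $5,000 added cost and half the excess retained. B.8 gives no added-cost figure and says only that it should be small relative to treatment. This is a cheap improvement.

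**What to change.** In D.12.6, define post-SVR mortality, cost and quality of life by fibrosis stage at cure, using the baseline stage already collected. A separate post-SVR decompensated state is needed only if the model allows cure at that stage.

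At minimum, pre-name a one-way and a probabilistic sensitivity analysis in which a fraction of the cirrhosis excess persists after SVR, with full return to uninfected values as one scenario. Report it for TAU against no treatment as well as for mDOT and CGT.

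The cost is some modelling work, a published input for the residual share, and possibly less favourable ratios. Enrolment, treatment, data collection, and the Aim 1 sample size and alpha do not change.

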D.12.4. Analytic plan for Aim 2. The proportion of participants (n=150) who develop resistance will be determined with 95% confidence interval (CIs) calculated using exact binomial methods. The proportion of participants with resistance will then be determined within each of 4 groups determined by quartiles of adherence measured at the final time point in the study. We will apply logistic regression models to estimate odds ratios for resistance in each quartile. To examine whether the relationship between adherence and resistance is quadratic, we will test a linearity of trends in odds ratios. If this linear trend is rejected, we will identify a quartile group that is associated with the highest odds of resistance. Potential covariates will be entered in regression models if found by univariate analysis to be associated ($p<0.2$) with resistance.

D.12.5. Hypotheses for Aim 3. We hypothesize that the total cost of delivering the CGT intervention will be lower than delivering the mDOT intervention, and that the incremental cost-effectiveness ratios for CGT v. TAU and mDOT v. TAU will each be less than \$100,000/QALY.

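### If the probabilistic sensitivity analysis summarises the ICER by median and interquartile range, those quantiles cannot be read against $100,000/QALY once the simulated QALY difference can change sign

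*Combined protocol and SAP*

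**What the plan says.** Section D.12.6 defines the outputs of the cost-effectiveness model: "Primary outcomes will be projected life-expectancy, quality-adjusted life-expectancy (QALYs), lifetime costs, and incremental cost-effectiveness ratios". The ratios are in dollars per QALY, and "The resulting ratios will be compared to a threshold of \$100,000 per QALY". The section then turns to uncertainty. It plans one-way and two-way sensitivity analyses and "probabilistic sensitivity analyses (PSAs) using second order Monte Carlo simulation on multiple variables". On size, "For PSAs we will perform 1,000 simulations of a cohort of 100,000 individuals". On reporting, the 1,000 model outcomes are to be given as a distribution "with a median and interquartile range that reflects underlying uncertainty in critical model parameters".

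The Aim 3 hypothesis in D.12.5 is that the ratios for CGT v. TAU and "mDOT v. TAU will each be less than \$100,000/QALY". It sets no condition on the sign of the QALY difference.

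Neither section mentions net monetary benefit, the cost-effectiveness plane, an acceptability curve, the probability of being cost-effective, or how a negative ratio or a dominated draw is to be handled.

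**The concern.** A negative ICER has two opposite meanings. An arm that is cheaper and better has one, and so does an arm that is dearer and worse. When simulated QALY differences fall on both sides of zero, sorting the ratios mixes these cases, and a median or quartile of the sorted list no longer carries decision meaning. Set against a ceiling of $100,000/QALY, every dominated draw counts as a draw under the ceiling.

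The plan gives reasons to expect this. Trial SVR by arm feeds the model (D.12.6). All newly enrolled subjects receive a regimen with SVR above 95% (D.9.6), and D.13 says the effect size on it is likely to be lower. Arms have 50 subjects (D.7), and the 100 on the fixed-dose regimen come to 100/3, about 33 per arm. Section B.8 expects the extra cost of the intensive models to be relatively small compared with the cost of treatment. Small, imprecise SVR differences combined with a positive extra cost produce ratios that flip sign from draw to draw.

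At stake is how the uncertainty around Aim 3 is read: an arm with no benefit could be shown with an interquartile range lying wholly under the threshold.

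**Working it through.** **The plan's own figures.** The PSA text gives only the number of draws, the cohort size and the threshold, so it has no derived result to reproduce. As a side check on the SVR inputs in D.13, the omnibus three-arm chi-square test (2 df, alpha 0.05, 40 per arm, 70%/70%/40%) has 81.5% power, which agrees with the stated figure of more than 80%.

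**Definitions.** For an intensive arm against TAU, as in D.12.5:

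- dE = (QALYs per SVR) × (SVR intensive − SVR TAU)
- dC = extra cost per patient
- ICER = dC/dE
- net monetary benefit (NMB) = $100,000 × dE − dC

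**Two draws by hand**, with 2.0 QALYs per SVR and dC = $2,000:

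- SVR 1 point lower: dE = 2.0 × (−0.01) = −0.02; ICER = 2,000/(−0.02) = −$100,000; NMB = −2,000 − 2,000 = −$4,000.
- SVR 5 points lower: dE = 2.0 × (−0.05) = −0.10; ICER = 2,000/(−0.10) = −$20,000; NMB = −10,000 − 2,000 = −$12,000.

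Both draws are dominated and both sort below $100,000. The ratio also gives the less harmful draw the lower value, so its order carries no information about value. NMB orders the two correctly.

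**An identity.** When dC > 0, ICER < $100,000 holds if dE < 0 or if NMB > 0, and these two events are disjoint. The share of draws below the threshold is therefore the share dominated plus the true probability of being cost-effective.

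**Simulation.** The documents give no dollar or QALY inputs, so the following are assumptions: 50 per arm, beta-distributed SVR, 2.0 QALYs per SVR (SD 0.5), cost SD 20%, and 1,000,000 draws. Ranges reflect the choice of beta prior.

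| SVR TAU v intensive | Extra cost | ICER median | ICER IQR | P(cost-effective) |
|---|---|---|---|---|
| (a) 92% v 92% | $2,000 | near 0, sign unstable | about −$30,000 to +$30,000 | about 42% |
| (b) 92% v 94% | $5,000 | about $32,000–$36,000 | about −$54,000 to between $80,000 and $89,000 | about 44% |
| (c) 95% v 90% | $2,000 | negative | −$29,400 to −$7,700 | about 11% |
| (d) 40% v 70% | $2,000 | about $3,400 | $2,500 to $4,800 | 99.8% |

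- In (a), about 92% of draws lie below $100,000. By the identity this is about 50% dominated plus 42% cost-effective.
- In (b), the ratio of means is about $126,000–$131,000/QALY. By hand, 5,000/(2.0 × 0.02) = $125,000. The whole IQR lies below the threshold although the ratio of means lies above it.
- In (c), 84% of draws are dominated, and 84% + 11% = 95% fall below the threshold.
- In (d), the planned effect, the quantiles do not mislead.

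**Sensitivity to cost.** At an extra $10,000 the upper quartile is about $140,000–$178,000 across (a) and (b), so the IQR no longer lies below the threshold. A separate run used gamma-distributed cost and QALYs, $500–$10,000, 1–5 QALYs per SVR, a saving per SVR of $0 or $20,000, and 33 or 50 per arm. The median ICER of 1,000 draws was below $100,000 in at least 93% of repeats in every scenario where the intensive arm had no effect or was worse.

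**The case against.** The strongest reply is that the PSA sentence speaks of model outcomes and never names the ICER. Three of the four listed outcomes (life expectancy, QALYs, lifetime costs) can be given a median and IQR without this problem. This stands to the extent that the point must be conditional. It does not remove the point, because the ICER is in the same section's outcome list, is not excepted, and is the outcome compared with the threshold.

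A reader might also infer that the Aim 3 conclusion itself will rest on an ICER median. The documents do not support that. The threshold comparison is described before the PSA and appears to concern the base-case ratios, while the PSA is introduced as a way to explore uncertainty. A base-case ICER with dominance checked would expose an ineffective arm, and the costs and QALYs are reported as well.

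A third reading, that the IQR will mislead whatever the inputs, is also too strong. The ordering problem is general once dE changes sign, but an IQR wholly under $100,000 appears only for some costs with small SVR differences. In (a) and (b) the IQR straddles zero, which would alert a careful reader. That does not help in (c), where the whole range is negative.

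Finally, covering the middle half of the draws is what an IQR does by definition. It is disclosed and is not an error in itself.

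**Conclusion.** The point holds in conditional form. If the ICER is among the outcomes given a median and IQR, as D.12.6 permits, those quantiles cannot be read against $100,000/QALY when the QALY difference may change sign. The plan's own expectation of high SVR and a smaller effect makes sign changes plausible. Under the stated assumptions, the share of draws apparently under the threshold can be about 92% when the probability of being cost-effective is about 42%. An IQR can also lie wholly under the threshold when the ratio of means is about $126,000–$131,000/QALY.

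The size of the distortion rests on cost and QALY inputs that the documents do not give. It vanishes at the planned 70% v 40%. The flaw is in the uncertainty summary and leaves the base-case comparison intact. It should be corrected before the analysis, but it does not invalidate Aim 3.

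**What to change.** Replace the PSA reporting sentence in D.12.6. From the same 1,000 simulations, report for each intensive model:

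- mean incremental cost and mean incremental QALYs;
- the ICER as the ratio of those means, with dominance labelled;
- incremental net monetary benefit at $100,000/QALY, with a 95% interval;
- the probability that each model is cost-effective, as an acceptability curve.

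State that no quantiles of the ICER will be taken. Medians may stay for costs, QALYs and life expectancy, with 95% intervals. If ICER quantiles were never intended, say so in one sentence and still add the net-benefit summary.

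The cost is a change of wording and slightly more analysis work. No new data or simulations are needed.
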